## 9.1.2.2. Baseline Visit (Day 1)

The investigator must have received all results from the screening visit before proceeding with the baseline visit. Once eligibility has been confirmed, the investigator will randomize the subject using IWRS prior to or during the baseline visit. The subject must complete all baseline procedures before being dispensed the study drug. The following procedures are to be completed and documented at the baseline visit.

- Review of AEs and changes in concomitant medications.
- Complete physical examination (urogenital/anorectal examinations will be performed at the discretion of the investigator).
- Vital signs measurement (blood pressure and pulse) and weight.
- Midstream urine sample collection for the following laboratory procedures:
  - Urinalysis and urine chemistry (see also Section 9.1.2.1).
  - Urine renal biomarkers (fasted, ie, no food or drinks, except water, at least 8 hours prior to urine collection): RBP and beta-2-microglobulin. If the subject has not fasted prior to the visit, the visit may proceed, but the subject must return within 72 hours in a fasted state to provide a urine sample for renal biomarkers.
  - Urine pregnancy test (females of childbearing potential only). If the urine pregnancy test is positive at baseline, study drug will not be dispensed. The positive result will be confirmed with a serum pregnancy test. If the serum pregnancy test is positive, the subject will not be able to participate.

- Blood sample collection for the following laboratory analyses:
  - Chemistry profile (see also Section 9.1.2.1). At baseline, glucose will be performed as part of the metabolic profile.
  - Metabolic profile (collected fasted): total, high-density lipoprotein (HDL) and lowdensity lipoprotein (LDL) cholesterol, triglycerides, glucose. If the subject has not fasted prior to the visit, the visit may proceed, but the subject must return within 72 hours in a fasted state to have a blood draw for the metabolic assessments.
  - Cystatin C and eGFRcyst according to the CKD-EPI formula.
  - eGFRcr according to the Cockcroft-Gault formula and the CKD-EPI formula; for details, see Section 9.5.4.
  - Hematology profile.
  - Plasma HIV-1 RNA.
  - CD4+ cell count.
  - Plasma storage samples for possible additional testing.
  - PBMC storage sample that will only be analyzed if deemed necessary by the study virologist to characterize archived viral resistance.
- Study drug dispensation (D/C/F/TAF or bPI+FTC/TDF) in an open-label fashion:
  - Subjects in the investigational treatment arm must initiate dosing with D/C/F/TAF within 24 hours after the baseline visit.
  - Subjects in the control arm should be instructed to continue their current regimen consisting of a bPI + FTC/TDF.
  - Subjects should be counseled regarding the importance of adherence, and be instructed to bring unused medication and empty packaging to the unit at each visit.
- Dispensation of the study medication log booklet, in which subjects should record their missed study medication intakes. Subjects should also be instructed to bring their log booklet at each study visit.

In subjects participating in the bone investigation substudy:

- Bone biomarkers (collected fasted, ie, no food or drinks, except water, at least 8 hours prior to sample collection): C-type collagen sequence (CTX), procollagen type 1 N-terminal propeptide (P1NP), parathyroid hormone (PTH), and 25-hydroxy vitamin D. If the subject has not fasted prior to the visit, the visit may proceed but the subject must return within 72 hours in a fasted state to provide a blood sample for bone biomarker assessment.
- DXA scan of spine and hip: The scan is to be performed between the screening and the baseline visit (a window of +2 weeks is allowed) as long as eligibility has been confirmed. A rescan for technical reasons is allowed within 2 weeks.

## 9.1.3. Treatment Period

After the baseline visit, subjects will return for study visits at the end of Weeks 2, 4, 8, 12, 24, 36, and 48 (scheduled relative to the baseline visit date). The time window for the Week 2 visit is  $\pm 2$  days, and for the visits through Week 48 is  $\pm 7$  days of the protocol-specified visit date. The total treatment duration at the end of the treatment period should be 48 weeks. The following procedures are to be completed and documented at each visit.

- Review of AEs and changes in concomitant medications.
- Complete physical examination at **Weeks 24 and 48** (urogenital/anorectal examinations will be performed at the discretion of the investigator).
- Symptom-directed physical examination (physical examination of body parts for which symptoms have been reported by the subject) as needed at Weeks 2, 4, 8, 12, and 36.
- Vital signs measurement (blood pressure and pulse) and weight.
- Midstream urine sample collection for the following laboratory procedures:
  - Urinalysis and urine chemistry (see also Section 9.1.2.1).
  - Urine renal biomarkers (fasted, ie, no food or drinks, except water, at least 8 hours prior to urine collection; if the subject has not fasted prior to the visit, the visit may proceed, but the subject must return within 72 hours in a fasted state to provide a urine sample for renal biomarkers) at **Weeks 2, 4, 12, 24, and 48** (see also Section 9.1.2.2).
  - Urine pregnancy test (females of childbearing potential only); positive urine pregnancy tests will be confirmed with a serum test; if this test is positive, the subject will be withdrawn (see also Section 12.4.3).
- Blood sample collection for the following laboratory analyses:
  - Chemistry profile (see also Section 9.1.2.1). At Weeks 24 and 48, analysis of glucose will be done as part of the fasting metabolic profile and not as part of the chemistry profile.
  - Metabolic profile (including glucose; collected fasted; if the subject has not fasted prior to the visit, the visit may proceed, but the subject must return within 72 hours in a fasted state to have a blood draw for the metabolic assessments) at **Weeks 24 and 48** (see also Section 9.1.2.2).
  - Cystatin C and eGFRcyst according to the CKD-EPI formula.
  - eGFRcr according to the Cockcroft-Gault formula, and the CKD-EPI formula (for details, see Section 9.5.4).
  - Hematology profile (see also Section 9.1.2.1).
  - Plasma HIV-1 RNA.
  - CD4+ cell count.

- Blood sample for HIV-1 resistance testing. For subjects with confirmed HIV-1 RNA ≥50 copies/mL and a HIV-1 RNA value ≥400 copies/mL, HIV-1 genotypic resistance test will be performed; phenotypic resistance test may be done upon request of the study virologist.
- Plasma storage sample for possible additional clinical testing.
- PBMC storage sample at Weeks 24 and 48, which will only be analyzed if deemed necessary by the study virologist to characterize archived viral resistance.
- Pharmacokinetic sample collection for D/C/F/TAF arm only:
  - Blood samples will be collected at Weeks 2, 4, 8, 12, 24, 36, and 48. The sample will be taken at least 15 minutes postdose if the regular dosing time coincides with the study visit, or at any time during the visit if the dosing time does not coincide with the scheduled study visit.
- Document study drug dispensation and accountability for all study drugs dispensed.
- Checking of the study medication log booklet for review of treatment adherence.

In subjects participating in the bone investigation substudy:

- Bone biomarkers at Weeks 2, 4, 12, 24 and 48 (collected fasted, ie, no food or drinks, except water, at least 8 hours prior to sample collection): CTX and P1NP. Biomarkers PTH and 25-hydroxy vitamin D will be assessed at Weeks 24 and 48 only. If the subject has not fasted prior to the visit, the visit may proceed but the subject must return within 72 hours in a fasted state to provide a blood sample for bone biomarker assessment.
- DXA scan of spine and hip at Weeks 24 and 48 (±10 days). A rescan for technical reasons is allowed within 2 weeks.

## 9.1.4. Extension Phase

Provided results from the DMC analyses or Week 24 interim analysis does not preclude (further) exposing subjects to D/C/F/TAF, subjects from the D/C/F/TAF arm will enter in the extension phase once they have completed their Week 48 visit. In addition, subjects in the control arm will receive the D/C/F/TAF tablet in the extension phase if, according to the investigator they will benefit from it and if all conditions are fulfilled (which includes adequate viral load results). Subjects from the control arm will be required to attend a switch visit at Week 52 to receive D/C/F/TAF. All subjects in the extension phase will have to attend visits every 12 weeks up to Week 96. As from Week 96, all subjects are offered the possibility to continue D/C/F/TAF treatment, if they wish and if they continue to benefit from it, until D/C/F/TAF becomes commercially available and is reimbursed, or can be accessed through another source in the country where he/she is living, or until the sponsor terminates clinical development. After Week 96, subjects should attend visits every 6 months. The time window for these visits is  $\pm 7$  days of the protocol-specified visit date.

Subjects from the control arm must have a Week 52 visit (switch visit) to allow providing D/C/F/TAF to subjects likely to benefit from it, based on the investigator's medical judgment. No investigations are foreseen during this visit, except for a blood sample collection to determine plasma HIV-1 RNA for those subjects that had HIV-1 RNA  $\geq$ 50 copies/mL at Week 48 and at the subsequent unscheduled visit. Information on concomitant medications, adherence and any AEs are to be collected during that visit.

In the extension phase, the following evaluations are to be completed and documented at each visit (except for the Week 52 switch visit).

- Review of AEs and changes in concomitant medications.
- Symptom-directed physical examination (physical examination for which symptoms have been reported by the subject) as needed at Weeks 60, 72, 84, 96 and every 6 months after Week 96.
- Vital signs measurement (blood pressure and pulse) and weight.
- Midstream urine sample collection for the following laboratory procedures:
  - Urinalysis and urine chemistry (see also Section 9.1.2.1).
  - Urine renal biomarkers (fasted, ie, no food or drinks, except water, at least 8 hours prior to urine collection; if the subject has not fasted prior to the visit, the visit may proceed, but the subject must return within 72 hours in a fasted state to provide a urine sample for renal biomarkers) at **Week 96** only (see also Section 9.1.2.2).
  - Urine pregnancy test (females of childbearing potential only); positive urine pregnancy tests will be confirmed with a serum test. If the test is positive, the subject will be withdrawn (see also Section 12.4.3).
- Blood sample collection for the following laboratory analyses:
  - Chemistry profile (see also Section 9.1.2.1).
  - Metabolic profile (including glucose; collected fasted; if the subject has not fasted prior to the visit, the visit may proceed, but the subject must return within 72 hours in a fasted state to have a blood draw for the metabolic assessments) at **Week 96** only (see also Section 9.1.2.2).
  - Cystatin C and eGFRcyst according to the CKD-EPI formula at Week 96 only.
  - eGFRcr according to the Cockcroft-Gault formula and the CKD-EPI formula (for details, see Section 9.5.4).
  - Hematology profile (see also Section 9.1.2.1).
  - Plasma HIV-1 RNA.
  - CD4+ cell count.
  - Blood sample for HIV-1 resistance testing. For subjects with confirmed HIV-1 RNA  $\geq$ 50 copies/mL and with a HIV-1 RNA value  $\geq$ 400 copies/mL, HIV-1 genotypic

resistance test will be performed; phenotypic resistance test may be done upon request of the study virologist.

- Plasma storage sample for possible additional clinical testing at Week 96 only.
- PBMC storage sample at **Week 96** only, which will only be analyzed if deemed necessary by the study virologist to characterize archived viral resistance.
- Document study drug dispensation and accountability for all study drugs dispensed.

In subjects participating in the bone investigation substudy:

- Bone biomarkers at Week 96 (collected fasted, ie, no food or drinks, except water, at least 8 hours prior to sample collection): CTX, P1NP, PTH, and 25-hydroxy vitamin D. If the subject has not fasted prior to the visit, the visit may proceed but the subject must return within 72 hours in a fasted state to provide a blood sample for bone biomarker assessment.
- DXA scan of spine and hip at Week 96 (±10 days). A rescan for technical reasons is allowed within 2 weeks.

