# TIME AND EVENTS SCHEDULE

Period				48-Weeks Treatment Period c							Extensio				
		Baseline	Week	Week	Week	Week	Week	Week	Week	Week	Every	Week	Every		30-Day
Visit	Screening a	Day 1 b	2	4	8	12	24	36	48	52 e	12 Weeks	96	6 months	$\mathbf{ESTD}^{\mathrm{f}}$	FUg
Study Procedures			•		•	•		•							
Screening/Administrative															
Informed consent h	Х														
Medical history	Х														
12-Lead ECG	X														
Height	X														
HBV and HCV testing	X														
Serum pregnancy test 	X														
FSH test j	Х														
Inclusion/exclusion criteria	Х														
Check clinical status		X k													
Study Drug Administration															
Randomization 		Х													
Adherence (log booklet) m		Х	Х	Х	Х	Х	Х	Х	Х	Х	Х	Х			
Drug dispensation &															
accountability		Х	X n	Х	Х	Х	Х	Х	Х	Х	Х	Х	Х	$X^n$	
Safety Evaluations															
Vital signs and weight	Х	Х	Х	Х	Х	Х	Х	Х	Х		Х	Х	Х	Х	X°
Complete physical															
examination	Х	Х					Х		Х					Х	
Symptom-directed physical															
examination			Х	Х	Х	Х		Х			X p	$X^p$	X p		Х
Concomitant medications	Х	Х	Х	Х	Х	Х	Х	Х	Х	Х	Х	Х	Х	Х	Х
Adverse events (AEs)	Х	Х	Х	Х	Х	Х	Х	Х	Х	Х	Х	Х	Х	Х	Х
Clinical Laboratory Tests q															
Chemistry profile r	Х	Х	Х	Х	Х	Х	Х	Х	Х		Х	Х	Х	Х	Х
Metabolic profile s		Х					Х		Х			Х			
Hematology profilet	Х	Х	Х	Х	Х	Х	Х	Х	Х		Х	Х	Х	Х	Х
Cystatin C and eGFRcyst	Х	Х	Х	Х	Х	Х	Х	Х	Х			Х			
eGFRcr u	Х	Х	Х	Х	Х	Х	Х	Х	Х		Х	Х	Х	Х	Х
Urinalysis and urine															
chemistry v	Х	Х	Х	Х	Х	Х	Х	Х	Х		Х	Х	Х	Х	Х
Urine pregnancy test 		Х	Х	Х	Х	Х	Х	Х	Х		Х	Х	Х	Х	Х
Renal biomarkers w		Х	Х	Х		Х	Х		Х			Х		Х	

Period				48-Weeks Treatment Period °						Extension Phase d					
		Baseline									•	Week	•	nampf	30-Day
Visit	Screening a	Day 1 b	2	4	8	12	24	36	48	52 e	12 Weeks	96	6 months	ESTD 	FU g
Study Procedures															
Efficacy Evaluations															
Plasma HIV-1 RNA x	Х	Х	Х	Х	Х	Х	Х	Х	X y		Х	Х	Х	Х	Х
CD4+ cell count	Х	Х	Х	Х	Х	Х	Х	Х	Х		Х	Х	Х	Х	Х
HIV-1 genotype/phenotype z			Х	Х	Х	Х	Х	Х	Х		Х	Х	Х	Х	
PBMC sample aa		Х					Х		Х			Х		Х	
Bone investigation															
substudy															

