Bone biomarkers bb		Х	Х	Х		Х	Х		Х			Х		Х	
DXA scans cc		Х					Х		Х			Х		Х	
Pharmacokinetic															
Evaluations															
Pharmacokinetic sample dd			Х	Х	Х	Х	Х	Х	Х					Х	
Other															
Plasma sample storage ee		Х	Х	Х	Х	Х	Х	Х	Х			Х		Х	

DXA: dual energy x-ray absorptiometry; ECG: electrocardiogram; ESTD: Early Study Treatment Discontinuation visit; FSH: follicle-stimulating hormone; FU: Follow-up; HBV: hepatitis B; HCV: hepatitis C; PBMC: peripheral blood mononuclear cells.

- a Evaluations to be completed within 30 days prior to baseline (Day 1). The screening period may be extended on a case-by-case basis after discussion with the sponsor; however, no extensions beyond 6 weeks will be allowed.
- b The baseline visit (Day 1) cannot proceed until the investigator has received all results of the screening visit and subject eligibility has been confirmed. Subjects will be dispensed investigational drug on the baseline visit; initiation of treatment with the investigational drug must take place within 24 hours after the baseline visit.
- c All study visits are to be scheduled relative to the baseline visit date and are to occur at the end of Weeks 2, 4, 8, 12, 24, 36, 48. The visit window is ±2 days of the protocol-specified date at Week 2, ±7 days of the protocol-specified date through Week 48.
- d Study visits during the extension phase are to be completed within  $\pm 7$  days of the protocol-specified visit date. Visits in the extension phase will occur every 12 weeks up to Week 96 and every 6 months thereafter, until D/C/F/TAF becomes commercially available and is reimbursed, or can be accessed through another source in the country where he/she is living, or until the sponsor terminates clinical development.
- e Visit only applicable for subjects from the control arm to allow them to switch to D/C/F/TAF. At this visit, the D/C/F/TAF tablets will be dispensed to those subjects. Subjects in the control arm will receive the D/C/F/TAF tablets in the extension phase if, according to the investigator they will benefit from it and if all conditions are fulfilled (which includes adequate viral load results).

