If dipstick result is abnormal, flow cytometry will be used to measure sediment. In case of discordance between the dipstick results and the flow cytometric results, the sediment will be examined microscopically. In the microscopic examination, observations other than the presence of WBC, RBC and casts may also be reported by the laboratory.

- Urine renal biomarkers: RBP and beta-2-microglobulin (collected fasted).
- Cystatin C.
- Serum Chemistry panel: ALP, AST, ALT, GGT, total bilirubin, direct and indirect bilirubin, total protein, albumin, CPK, bicarbonate, BUN, chloride, creatinine, glucose, phosphorus, potassium, sodium, uric acid, and amylase (reflex lipase testing is performed in subjects with total amylase >1.5 x ULN), and AAG.

At baseline, Weeks 24, 48, and every 24 weeks during the extension phase, analyses of glucose will be done as part of the fasting metabolic assessments and not as part of the chemistry profile.

For the calculation of eGFRcr according to the Cockcroft-Gault and CKD-EPI formulas, and eGFRcyst according to the CKD-EPI formula see Section 9.5.4; the eGFR calculations will be performed by the central laboratory.

- Metabolic panel: total, HDL and LDL cholesterol, triglycerides, glucose; (collected fasted).
- Hematology panel: hemoglobin, hematocrit, RBC count and parameters (MCH, MCH concentration and MCV), WBC count with differential (neutrophils, lymphocytes, monocytes, eosinophils, basophils), and platelet count.
- Pregnancy testing: The screening sample for biochemistry will include a serum pregnancy test for all female subjects of childbearing potential; a urine pregnancy test will be performed at all other visits. Positive urine pregnancy tests will be confirmed with a serum pregnancy test. FSH testing is required for female subjects who have stopped menstruating for at least 2 years but do not have documentation of ovarian hormonal failure. The results of the serum and urine pregnancy tests should be recorded in the eCRF and in the subject's medical records.
- Hepatitis testing: A sample will be taken for HBV and HCV testing (HBsAg, HCV RNA, and HCV antibody) at screening. Whenever clinically relevant, the investigator can request additional tests at other visits.
- Bone biomarkers: CTX, P1NP, PTH, and 25-hydroxy vitamin D (collected fasted) (only for subjects participating in the bone investigation substudy).

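### Minor: Week 52, where control subjects receive their first D/C/F/TAF, is the only dispensing visit without a scheduled urine pregnancy test

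*Protocol*

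**What the plan says.** The switch visit is a dispensing visit. Footnote e of the Time and Events Schedule says of control subjects moving to the extension: "At this visit, the D/C/F/TAF tablets will be dispensed to those subjects".

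Section 9.1.4 limits what is done there: "No investigations are foreseen during this visit, except for a blood sample collection to determine plasma HIV-1 RNA for those subjects that had" 50 copies/mL or more at Week 48 and at the unscheduled visit that followed. It adds only that concomitant medications, adherence and adverse events are recorded. Its list of extension-phase evaluations, which "are to be completed and documented at each visit (except for the Week 52 switch visit"), includes the urine pregnancy test. In the schedule, the row "Urine pregnancy test" is blank at Week 52.

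Elsewhere the test is routine. Section 9.1.3 has it at each visit through Week 48 and states that "positive urine pregnancy tests will be confirmed with a serum test; if this test is positive, the subject will be withdrawn". Section 12.4.3 also requires prompt withdrawal of a subject who becomes pregnant. At Day 1, Section 9.1.2.2 says: "If the urine pregnancy test is positive at baseline, study drug will not be dispensed".

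Section 9.4.2 is ambiguous for Week 52. Its paragraph on pregnancy testing says that, apart from the serum test at screening, "a urine pregnancy test will be performed at all other visits". Its opening paragraph sends the timing of urine pregnancy testing to the Time and Events Schedule.

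**The concern.** The protocol does not allow pregnant subjects to stay on study treatment, and it tests for pregnancy at every other visit where drug is handed out. The one omission falls where control subjects start the investigational regimen. A pregnancy that becomes detectable between Week 48 and Week 52 would not be found by a scheduled test before the first D/C/F/TAF dose, and no further scheduled test follows until Week 60.

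The text also gives sites two answers. A site reading the pregnancy paragraph of Section 9.4.2 would test at Week 52. A site working from the schedule or Section 9.1.4 would not.

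What is at stake is subject safety and consistent conduct. No efficacy endpoint depends on the pregnancy test.

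**Working it through.** **Schedule columns.** After screening, the schedule has these columns: Day 1; Weeks 2, 4, 8, 12, 24, 36, 48, 52; every 12 weeks; Week 96; every 6 months; ESTD; 30-day follow-up. That is 14.

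- Urine pregnancy test marked: 13 of 14. The blank is Week 52.
- Dispensing columns: the dispensation and accountability row is marked in all of these except the 30-day follow-up, giving 13. Footnote n makes Week 2 and ESTD accountability only, so 13 − 2 = 11.
- Dispensing columns with the test marked: 10 of 11. The exception is again Week 52.

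The blank is not an artefact of how the table was read. Section 9.1.4 independently excludes Week 52 from the list that contains the test.

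**Intervals.** Visits are timed from baseline, with ±7 days for Week 48 (footnote c) and for extension visits (footnote d). The first 12-weekly extension visit is Week 60.

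| Interval | Nominal | Range with ±7 days at each end |
|---|---|---|
| Week 48 test to Week 52 dispensing | 4 × 7 = 28 days | 28 − 14 = 14 to 28 + 14 = 42 |
| Week 52 dispensing to Week 60 test | 8 × 7 = 56 days | 56 − 14 = 42 to 56 + 14 = 70 |
| Week 48 test to Week 60 test | 28 + 56 = 84 days (12 weeks) | 84 − 14 = 70 to 84 + 14 = 98 |

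**Comparison with accepted gaps.** Weeks 12 to 24, 24 to 36 and 36 to 48 are each 12 × 7 = 84 days, and the 12-week interval continues to Week 96. After that the interval is 6 months. The 84 days between the Week 48 and Week 60 tests are therefore no longer than the gaps accepted during ongoing treatment.

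**Comparison with Day 1.** Footnote a describes screening as "Evaluations to be completed within 30 days prior to baseline (Day 1"), with no extension beyond 6 weeks (6 × 7 = 42 days). The screening serum test may thus be up to 30 days old, or 42 at most, and it is still followed by a urine test before dispensing. At Week 52 a result of similar age, nominally 28 days, is not followed by one.

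**HIV-1 RNA row.** This row is also blank at Week 52, although Section 9.1.4 orders a draw there for controls at or above 50 copies/mL twice. Footnote y covers only the retest within 3 weeks of Week 48. This is a mismatch between schedule and text.

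**The case against.** The strongest reply is that the omission is deliberate and adds little risk. The synopsis, Section 3.1, the schedule and Section 9.1.4 all treat Week 52 as a light visit. Inclusion criterion 11 requires contraception or abstinence, schedule footnotes allow extra pregnancy tests at the investigator's discretion, and these women are already taking antiretrovirals. The D/C/F/TAF arm, dispensed at Week 48, is also next tested at Week 60. All of this stands and keeps the point minor. It does not settle the conflict with Section 9.4.2, and a discretionary test is not the scheduled check used at every other dispensing visit.

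Two stronger readings are tempting, and the documents support neither.

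- A reader might infer that Week 52 breaks a first-dose rule set at Day 1. The Day 1 test is also an enrolment check. Pregnancy is an exclusion criterion, and the test applies to both arms, including controls who simply continue their regimen. The analogy is only partial.
- A reader might infer that controls with unresolved viraemia would be switched on a viral load result that is not yet known. Section 9.1.4 already makes the switch conditional on adequate viral load, and footnote y requires a return to an acceptable level first. Nothing says that the Week 52 draw decides dispensing on the day, and no laboratory turnaround time is given. The lack of a numerical cut-off is missing detail and is not part of this point.

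**Conclusion.** The point holds as a minor one. Week 52 is the only one of 11 dispensing columns with no scheduled urine pregnancy test, and it is the visit at which control subjects begin the investigational tablet. Followed as scheduled, the plan starts that tablet on a test nominally 28 days old (14 to 42), with the next test nominally 56 days later (42 to 70). Section 9.4.2 can be read as requiring the test, so the text should be reconciled in any case.

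The day ranges assume that Week 52 carries the ±7-day window given for extension visits. Only women of childbearing potential in the control arm who switch are affected; the documents do not give their number, so no expected count of missed pregnancies can be calculated.

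The Week 48 primary comparison is not affected. The unmarked HIV-1 RNA draw is a housekeeping matter only, because Section 9.1.4 already orders it.

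**What to change.** In Section 9.1.4, add a urine pregnancy test before dispensing at Week 52 for women of childbearing potential. If it is positive, D/C/F/TAF is not dispensed and the result is confirmed by a serum test. Mark the test at Week 52 in the Time and Events Schedule. The schedule, Section 9.1.4 and Section 9.4.2 then agree.

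In the same amendment, add a Week 52 footnote to the HIV-1 RNA row for the conditional draw that Section 9.1.4 already requires.

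The cost is a few lines of amendment text and one inexpensive urine test at a visit the subject already attends.
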